#### **9.5.2.3 Vital signs**

Analysis of the vital sign measurements using summary statistics for the change from Baseline for each post-Baseline visit will be performed. These descriptive summaries will be

presented by vital sign and treatment group. Change from Baseline will only be summarized for patients with both a Baseline and post-Baseline value.

## **9.6 Analysis of exploratory variables**

All endpoints relating to exploratory objectives will be summarized descriptively. Summary statistics will include relative and absolute frequencies for the categorical variables and the number of patients, minimum, mean, median and maximum for continuous variables. Time courses of response rates and mean NRS-scores will be displayed graphically. Inferential statistical test may be calculated as appropriate, they will use the same methodology as described for the primary endpoint. Details will be specified in the Statistical Analysis Plan.

## **9.7 Interim analyses**

No interim analysis is planned for this study.

## **9.8 Sample size calculation**

To assess the assumed effect size at Week 8, a 43.6% response rate (NRS < 4) is assumed for the secukinumab 150 mg group. This number is derived as an average of the response rates observed in the CAIN457F2320 and CAIN457F2310 studies (Baeten et al 2015). For the placebo group, a response rate at Week 8 of 23.5% (NRS < 4) was selected as assessed in the CAIN457F2320 study. This intermediate scenario takes into consideration a certain likelihood of a relatively high placebo response also in line with data from the TNF $\alpha$  reference studies and the CAIN457F2305 study in addition to the slightly milder course of the disease in the studied population (Baeten et al 2015).

Assuming conservatively a response rate of 23.5% in the placebo group and a response rate of 43.6% under secukinumab 150 mg, 332 patients in total (i.e. 249 patients in secukinumab 150 mg group and 83 patients in placebo group) would be needed under 3:1 (secukinumab: placebo) allocation to achieve 90% power on a (2-sided) 5% significance level. To compensate for drop-out patients or those with protocol deviations, a total of 352 patients (264 in secukinumab 150 mg group and 88 in the placebo group) should be recruited.

## **10 Ethical considerations**

### **10.1 Regulatory and ethical compliance**

This clinical study was designed and shall be implemented, executed and reported in accordance with the International Conference on Harmonization of Technical Requirements for Registration of Pharmaceuticals for Human Use (ICH) Harmonized Tripartite Guidelines for GCP, with applicable local regulations (including European Directive 2001/20/EC, US CFR 21, and Japanese Ministry of Health, Labor, and Welfare), and with the ethical principles laid down in the Declaration of Helsinki.

### **10.2 Informed consent procedures**

Eligible patients may only be included in the study after providing written (witnessed, where required by law or regulation), IRB/IEC-approved informed consent, or, if applicable after

such consent has been provided by a legally acceptable representative(s) of the patient. In cases where the patient's representative gives consent, the patient must be informed about the study to the extent possible given his/her understanding. If the patient is capable of doing so, he/she must indicate assent by personally signing and dating the written informed consent document or a separate assent form. Informed consent must be obtained before conducting any study-specific procedures (e.g. all of the procedures described in the protocol). The process of obtaining informed consent must be documented in the patient source documents.

Novartis will provide to investigators in a separate document a proposed informed consent form that complies with the ICH GCP guideline and regulatory requirements and is considered appropriate for this study. Any changes to the proposed consent form suggested by the investigator must be agreed to by Novartis before submission to the IRB/IEC, and a copy of the approved version must be provided to the Novartis monitor after IRB/IEC approval.

Women of childbearing potential must be informed that taking the study treatment may involve unknown risks to the fetus if pregnancy were to occur during the study and agree that in order to participate in the study they must adhere to the contraception requirement for the duration of the study. If there is any question that the patient will not reliably comply, they must not be entered in the study.

In the event that Novartis wants to perform testing on the samples that are not described in this protocol, additional IRB/IEC approval will be obtained.

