
Exclusion criteria
	
Patients fulfilling any of the following criteria are not eligible for inclusion in this study. No additional exclusions may be applied by the investigator in order to ensure that the study population will be representative of all eligible patients.
 
 
1. Chest X-ray or magnetic resonance imaging (MRI) with evidence of ongoing infectious or malignant process obtained within 3 months of Screening and evaluated by a qualified physician (otherwise chest X-ray or MRI is required to be performed at Screening).
 
2. Previous treatment with prohibited medication as outlined in Section 5.5.7 and Section 5.5.8 of the main protocol. Prohibited medication may be washed out before randomization in accordance with Section 5.5.7 and Section 5.5.8 of the main protocol.
 
3. Previous exposure to secukinumab or any other biologic drug directly targeting interleukin-17 (IL-17) or interleukin-23 (IL-23).
 
4. Use of any investigational drug and/or devices within 4 weeks of randomization, or a period of 5 half-lives of the investigational drug, whichever is longer.
 
5. History of hypersensitivity to the study drug or its excipients or to drugs of similar chemical classes.
 
6. Patients previously treated with any biological immunomodulating agents, except those targeting TNF<math>\alpha</math>.
 
7. Patients who have been exposed to more than one anti-tumor necrosis factor alpha (anti-TNF<math>\alpha</math>) agent
 
8. Previous treatment with any cell-depleting therapies including but not limited to anti-cluster of differentiation (CD)20 or investigational agents (e.g. Campath®, anti-CD4, anti-CD5, anti-CD3, anti-CD19).
 
9. Pregnant or nursing (lactating) women, where pregnancy is defined as the state of a female after conception and until the termination of gestation, confirmed by a positive human chorionic gonadotropin (hCG) laboratory test.
 
10. Women of childbearing potential, defined as all women physiologically capable of becoming pregnant, unless they are using effective methods of contraception during entire study or longer if required by locally approved prescribing information (e.g. 20 weeks since last dose of secukinumab in the European Union (EU)). Effective contraception methods include: 
 
• Total abstinence, when this is in line with the preferred and usual
 
 
 

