- **Group A:** secukinumab 150 mg (1 x 1.0 mL) s.c. administered at Baseline, Week 1, 2, 3 and 4
- **Group B:** placebo (1 x 1.0 mL) s.c. administered at Baseline and Week 1, 2, 3 and 4

Secukinumab 150 mg and matching placebo will be provided as 1.0 mL pre-filled syringes (PFSS).

### 3.1.2 Treatment Period 2

At Week 8, patients will enter Treatment Period 2 (Week 8 to Week 24). Patients randomized to Group A (secukinumab 150 mg) at Baseline will be assessed for the achievement of spinal pain NRS score and will be classified as responders (spinal pain NRS score < 4) or non-responders (spinal pain NRS score  $\geq$  4). Responders will be re-assigned to 1 treatment arm (Arm A1) to continue double-blind treatment with secukinumab 150 mg every 4 weeks from Week 8 to Week 24 (last dose administered at Week 20). Non-responders will be separately re-randomized to 1 of 2 arms to receive double-blind treatment with either secukinumab 150 mg or secukinumab 300 mg every 4 weeks starting at Week 8 up to Week 24 (last dose administered at Week 20), as follows:

- Patients on secukinumab 150 mg who achieve spinal pain NRS score < 4 at Week 8 will be re-assigned to continue secukinumab 150 mg every 4 weeks (Arm A1)
  - **Arm A1:** secukinumab 150 mg (1 x 1.0 mL) plus placebo (1 x 1.0 mL) administered at Week 8, 12, 16 and 20
- Patients on secukinumab 150 mg who do not achieve spinal pain NRS score < 4 at Week 8 will be re-randomized to continue secukinumab 150 mg every 4 weeks (Arm A2) or to escalate to secukinumab 300 mg every 4 weeks (Arm A3):
  - **Arm A2:** secukinumab 150 mg (1 x 1.0 mL) plus placebo (1 x 1.0 mL) administered at Week 8, 12, 16 and 20
  - **Arm A3:** secukinumab 300 mg (2 x 1.0 mL) administered at Week 8, 12, 16, and 20

At Week 8, patients randomized to Group B (placebo) at Baseline will be re-randomized to either secukinumab 150 mg every 4 weeks (Arm B1) or secukinumab 300 mg every 4 weeks (Arm B2):

- **Arm B1:** secukinumab 150 mg (1 x 1.0 mL) plus placebo (1 x 1.0 mL) administered at Week 8, 12, 16 and 20
- **Arm B2:** secukinumab 300 mg (2 x 1.0 mL) administered at Week 8, 12, 16, and 20

[figure not shown]
During the study, patients will be required to self-administer secukinumab or placebo at all study visits and at home at Week 16 (see [Table 6-1](#) and [Table 6-2](#) for the timing of study treatment administration).

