## 4.2 Exclusion criteria

Patients fulfilling any of the following criteria are not eligible for inclusion in this study. No additional exclusions may be applied by the investigator, in order to ensure that the study population will be representative of all eligible patients.

1. Chest X-ray or MRI with evidence of ongoing infectious or malignant process obtained within 3 months of Screening and evaluated by a qualified physician (otherwise chest X-ray or MRI is required to be performed at Screening).
2. Previous treatment with prohibited medication as outlined in Section 5.5.7 and Section 5.5.8. Prohibited medication may be washed out before randomization in accordance with Section 5.5.7 and Section 5.5.8.
3. Previous exposure to secukinumab or any other biologic drug directly targeting interleukin-17 (IL-17) or interleukin-23 (IL-23).
4. Use of any investigational drug and/or devices within 4 weeks of randomization, or a period of 5 half-lives of the investigational drug, whichever is longer.
5. History of hypersensitivity to the study drug or its excipients or to drugs of similar chemical classes.
6. Patients previously treated with any biological immunomodulating agents, except those targeting TNF $\alpha$ .
7. Patients who have been exposed to more than one anti-tumor necrosis factor alpha (anti-TNF $\alpha$ ) agent.
8. Previous treatment with any cell-depleting therapies including but not limited to anti-CD20 or investigational agents (e.g. Campath®, anti-CD4, anti-CD5, anti-CD3, anti-CD19).
9. Pregnant or nursing (lactating) women, where pregnancy is defined as the state of a female after conception and until the termination of gestation, confirmed by a positive human chorionic gonadotropin (hCG) laboratory test.
10. Women of childbearing potential, defined as all women physiologically capable of becoming pregnant, unless they are using effective methods of contraception during entire

study or longer if required by locally approved prescribing information (e.g. 20 weeks since last dose of secukinumab in the European Union (EU)). Effective contraception methods include:

- Total abstinence, when this is in line with the preferred and usual lifestyle of the patient. Periodic abstinence (e.g. calendar, ovulation, symptothermal, post-ovulation methods) and withdrawal are not acceptable methods of contraception.

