## **5.6 Study completion and discontinuation**

### **5.6.1 Study completion and post-study treatment**

A patient will be considered to have completed the study when the patient has completed the last visit planned in the protocol i.e. Visit 10/Week 24 (see [Table 6-1](#)). Information on the patient's completion or discontinuation from the study and the reason for discontinuation from the study will be recorded on the appropriate Study Phase Completion page in the eCRF. In any case, the investigator or site staff must contact the IRT as soon as possible to record the patient's study completion and/or discontinuation.

The investigator must provide follow-up medical care for all patients who are prematurely withdrawn from the study or must refer them for appropriate ongoing care. This care may include initiating another treatment outside of the study as deemed appropriate by the investigator. Based on the individual risk/benefit profile of a patient, treatment options may include DMARDs. In case of a biologic treatment, a waiting period of 3 months before initiating the treatment is recommended.

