Patients who prematurely discontinue the study should return and complete assessments associated with the Week 24 visit (4 weeks after the last study treatment, see [Table 6-1](#)) and any AEs that are treatment emergent should be reported until 12 weeks after the last study treatment. The final visit should be performed before any new treatment is initiated.

Patients who prematurely withdraw from the study will not be replaced.

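### Section 10.2 ties the fetal-risk warning and the contraception agreement to the study period, up to 16 weeks short of what exclusion criterion 10 requires under its own EU example

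*Protocol*

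**What the plan says.** Exclusion criterion 10, in the protocol summary and in section 4.2, excludes women of childbearing potential unless they use effective contraception during the entire "study or longer if required by locally approved prescribing information". Both places give 20 weeks since the last secukinumab dose in the EU as the example.

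Section 10.2 (Informed consent procedures) states what the same women must be told and must agree to. They are to be informed that "taking the study treatment may involve unknown risks to the fetus if pregnancy were to occur during the study", and to agree that "they must adhere to the contraception requirement for the duration of the study". Neither clause mentions a longer period, and neither refers to criterion 10.

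The end of the study is defined in section 5.6.1: "A patient will be considered to have completed the study when the patient has completed the last visit planned in the protocol", which is Visit 10 at Week 24. Section 3.1.2 places the end of dosing earlier ("last dose administered at Week 20"). For patients who stop early, section 5.6.2 asks for "assessments associated with the Week 24 visit (4 weeks after the last study treatment").

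On the form itself, section 10.2 says "Novartis will provide to investigators in a separate document a proposed informed consent form". That form is not among the documents reviewed.

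**The concern.** Criterion 10 treats the study and any longer labelled period as two different things. Section 10.2 picks up only the first. Where local labelling extends past the study, the protocol imposes a requirement but does not ask that the woman be told of its post-study part or agree to it.

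If the consent form follows section 10.2, a woman using a method she can stop (oral contraception, barrier methods, abstinence) could reasonably stop at Week 24 while still inside the period that criterion 10 sets. What is at stake is possible fetal exposure and the adequacy of consent. The primary endpoint, power, error rate and analysis are not affected.

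Little later in the protocol would catch the gap. Table 6-1 schedules the eligibility check only at Visits 1 and 2. Scheduled urine pregnancy tests end with the Week 24 visit. Section 7.6 words pregnancy reporting for patients on study drug. After Week 24, what the woman was told at consent is the main safeguard.

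**Working it through.** **Inputs**

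- Last dose: Week 20 (protocol 3.1.2).
- Patient's end of study: Visit 10, Week 24 (protocol 5.6.1).
- Final visit after early discontinuation: 4 weeks after the last dose (protocol 5.6.2).
- Adverse-event reporting: until 12 weeks after the last dose (protocol 5.6.2 and 7.1).
- Contraception under criterion 10, EU example: 20 weeks after the last dose (protocol summary and 4.2).

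**The plan's own interval**

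End of study minus last dose = 24 − 20 = 4 weeks. This matches the interval given in section 5.6.2.

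**End of the period required by criterion 10 (EU example)**

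Last dose + 20 = 20 + 20 = Week 40.

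**Shortfall in section 10.2**

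| Reading of the study period | Ends at | Weeks covered after last dose | Shortfall against 20 weeks |
|---|---|---|---|
| Completion as defined in 5.6.1 | Week 24 | 24 − 20 = 4 | 20 − 4 = 16 |
| Extended to the end of adverse-event reporting | 20 + 12 = Week 32 | 12 | 20 − 12 = 8 |
| Early discontinuer, final visit as in 5.6.2 | Last dose + 4 | 4 | 20 − 4 = 16 |

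The shortfall in the protocol text is therefore 8 to 16 weeks, and 16 weeks on the protocol's own definition of completion.

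**Does the EU example apply to this trial?**

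SAP section 2.5.2 groups countries with small numbers of subjects for the primary model. The list includes Ireland, Italy, Spain, Croatia, Belgium, Finland, Sweden, Lithuania, Latvia and Estonia, so it does.

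**Is the short wording confined to section 10.2?**

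No. In SAP section 5.5 the deviation entry for this criterion (EXCL10) also describes contraception over the entire study without the extension. This does not show what the consent form says.

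**The case against.** The strongest reply is that the operative rule is present, correct and stated twice. Section 10.2 sets no contraception rule of its own; it refers to the contraception requirement, and the only such requirement is criterion 10. It does not say that contraception may stop at Week 24, and a woman who follows criterion 10 also satisfies section 10.2. On this reading section 10.2 is incomplete but does not contradict criterion 10. The eligibility check at Visits 1 and 2 also obliges the investigator to look ahead to the whole required period.

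This does not cure the text. Criterion 10 itself separates the study from any longer period, so an agreement limited to the study's duration cannot carry the extension, even if the requirement it names is criterion 10. Compatibility is also not the test: section 10.2 defines what the woman is told and accepts, and an investigator could follow it to the letter without mentioning the period after Week 24. The same section bars women who may not reliably comply, but measures compliance against the shorter period.

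The second reply is that any harm depends on a form nobody here has seen. Section 10.2 says the form is to meet GCP and regulatory requirements, and section 10.3 requires ethics approval of both the protocol and the form. This stands in full. The form may already state the longer period, and nothing in the documents shows that any woman would be told to stop at Week 24.

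It also stands that the 16 weeks applies only where the label requires 20 weeks, and matters mainly for methods that can be stopped.

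**Conclusion.** The concern holds. Section 10.2 is wrong as written: its warning and its agreement both stop with the study, while criterion 10 extends further where local labelling requires. Under the EU example the text falls 16 weeks short (Week 24 against Week 40), or 8 weeks if the adverse-event window is counted as study time.

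Confidence in the mismatch is high because it rests on the protocol's own wording and dates. The practical effect is less certain. It is zero if the consent form already gives the longer period. Other labels would give a different gap, and the number of women affected is not stated in the documents. The sponsor should correct this; no result of the trial depends on it.

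**What to change.** Amend section 10.2 in two places:

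- Make the contraception agreement run for the study, or for longer where the local label requires it, with 20 weeks after the last dose in the EU as the example.
- Extend the fetal-risk statement to the same period.

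Then check that the model consent form states that period. The form check is the quicker step and shows whether any woman has been under-informed, so it should come first.

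The cost is two clauses in a written amendment, with the approvals that section 11.1 requires, and one document check. If the form proves short, it must be corrected and women already enrolled must be told. No visit, data item or analysis changes.

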### **10.3 Responsibilities of the investigator and institutional review board/independent ethics committee**

Before initiating a trial, the investigator/institution must obtain approval/favorable opinion from the IRB/IEC for the trial protocol, written informed consent form, consent form updates, patient recruitment procedures (e.g. advertisements) and any other written information to be provided to patients. Prior to study start, the investigator is required to sign a protocol signature page confirming his/her agreement to conduct the study in accordance with these documents and all of the instructions and procedures found in this protocol and to give access to all relevant data and records to Novartis monitors, auditors, Novartis Quality Assurance representatives, designated agents of Novartis, IRBs/IECs, and regulatory authorities as required. If an inspection of the clinical site is requested by a regulatory authority, the investigator must inform Novartis immediately that this request has been made.

### **10.4 Publication of study protocol and results**

Novartis assures that the key design elements of this protocol will be posted in a publicly accessible database such as [clinicaltrials.gov](http://clinicaltrials.gov). In addition, upon study completion and finalization of the study report the results of this trial will be either submitted for publication and/or posted in a publicly accessible database of clinical trial results.

### **10.5 Quality control and quality assurance**

Novartis maintains a robust Quality Management system that includes all activities involved in quality assurance and quality control, including the assignment of roles and responsibilities,

the reporting of results, and the documentation of actions and escalation of issues identified during the review of quality metrics, incidents, audits and inspections.

Audits of investigator sites, vendors, and Novartis systems are performed by Novartis Pharma Auditing and Compliance Quality Assurance, a group independent from those involved in conducting, monitoring or performing quality control of the clinical trial. The clinical audit process uses a knowledge/risk based approach.

Audits are conducted to assess GCP compliance with global and local regulatory requirements, protocols and internal standard operating processes, and are performed according to written Novartis processes.

## **11 Protocol adherence**

This protocol defines the study objectives, the study procedures and the data to be collected on study participants. Additional assessments required to ensure safety of patients should be administered as deemed necessary on a case by case basis. Under no circumstances is an investigator allowed to collect additional data or conduct any additional procedures for any research related purpose involving any investigational drugs under the protocol.

Investigators ascertain they will apply due diligence to avoid protocol deviations. If an investigator feels a protocol deviation would improve the conduct of the study this must be considered a protocol amendment, and unless such an amendment is agreed upon by Novartis and approved by the IRB/IEC and health authorities, where required, it cannot be implemented. All significant protocol deviations will be recorded and reported in the Clinical Study Report.

